6.4.4. Groups 1 and 2: Week 48 Assessments

Study Visit for Weeks 48 should be completed \pm 7 days of the protocol-specified visit date, based on the Baseline Visit. Group 2 subjects will follow local standard of care for renal monitoring. The following assessments and procedures will be performed and recorded on CRFs:

- Complete physical exam including vital signs, body weight and height
- Blood samples for:
 - Plasma HBV DNA (for PCR)
 - HBV serology (HBeAg and HBsAg; anti-HBe and anti-HBs (if HBsAg negative))
 - Hematology (CBC with differential and platelets, PT/INR)
 - Group 1: Serum renal chemistry (glucose, creatinine, creatinine clearance (calculated), magnesium, bicarbonate, chloride, potassium, sodium), fasting required
 - Liver chemistry (ALT, ALP, AST, total and direct bilirubin, total protein, albumin, GGT, LDH, CK), fasting required
 - Groups 1 and 2: Serum bone chemistry (calcium, phosphorus, 1,25 hydroxy vitamin D, PTH, osteocalcin, bone alkaline phosphatase, N and C telopeptides), fasting required
- Group 1: Urinalysis (glucose, protein, creatinine, phosphate, bicarbonate, blood, calcium), fasting required
- Groups 1 and 2: DEXA scan (+/- 14 days of the Week 48 visit) of spine and whole body
- Review of bone and renal AEs and any associated medical management
- Concomitant medications (including dietary supplements such as calcium, vitamin D, phosphorus)

- Assessment of medication adherence
- Tenofovir DF dispensing and instructions on appropriate dosing and administration
- Screening for pregnancy (urine screen)

Subjects who discontinue the study prior to the Week 48 Visit will complete all Week 48 assessments and procedures at an Early Drug Discontinuation Visit, to be completed within 72 hours of last dose of Tenofovir DF. Subjects who have received at least one dose of Tenofovir DF and permanently discontinue treatment will be followed for 24 weeks off treatment or up to initiation of an alternative treatment regimen, whichever occurs first.

6.4.5. Groups 1 and 2: Week 60 and 84 Assessments

Study Visit for Weeks 60 and 84 should be completed \pm 7 days of the protocol-specified visit date, based on the Baseline Visit. Group 2 subjects will follow local standard of care for renal monitoring. The following assessments and procedures will be performed and recorded on CRFs:

- Complete physical exam including vital signs, body weight and height
- Blood samples for:
 - Plasma HBV DNA (for PCR)
 - Group 1: Serum renal chemistry (glucose, creatinine, creatinine clearance (calculated), magnesium, bicarbonate, chloride, potassium, sodium), fasting required
- Group 1: Urinalysis (glucose, protein, creatinine, phosphate, bicarbonate, blood, calcium), fasting required
- Review of bone and renal AEs and any associated medical management
- Concomitant medications (including dietary supplements such as calcium, vitamin D, phosphorus)
- Assessment of medication adherence
- Tenofovir DF dispensing and instructions on appropriate dosing and administration
- Screening for pregnancy (urine screen)

Subjects who discontinue the study prior to the Week 60 or 84 Visit will complete all Week 60 or 84 assessments and procedures at an Early Drug Discontinuation Visit, to be completed within 72 hours of last dose of Tenofovir DF. Subjects who have received at least one dose of

Tenofovir DF and permanently discontinue treatment will be followed for 24 weeks off treatment or up to initiation of active treatment, whichever occurs first.

6.4.6. Groups 1 and 2: Week 96 Assessments/End of Treatment Visit

The Study Visit for Week 96/End of Treatment should be completed \pm 7 days of the protocol-specified visit date, based on the Baseline Visit. The following assessments and procedures will be performed and recorded on CRFs:

- Complete physical exam including vital signs, body weight and height
- Blood samples for:
 - Plasma HBV DNA (for PCR)
 - HBV serology (HBeAg and HBsAg; anti-HBe and anti-HBs (if Ag negative))
 - Hematology (CBC with differential and platelets, total and direct bilirubin, total protein, albumin, GGT, PT/INR)
 - Serum renal chemistry (glucose, creatinine, creatinine clearance (calculated), magnesium, bicarbonate, chloride, potassium, sodium), fasting required
 - Liver chemistry (ALT, ALP, AST, total and direct bilirubin, total protein, albumin, GGT, LDH, CK), fasting required
 - Serum bone chemistry (calcium, phosphorus, 1,25 hydroxy vitamin D, PTH, osteocalcin, bone alkaline phosphatase, N and C telopeptides), fasting required
- Urinalysis (glucose, protein, creatinine, phosphate, bicarbonate, blood, calcium), fasting required
- Groups 1 and 2: DEXA scan (+/- 14 days of the Week 96 visit) of spine and whole body
- Review of bone and renal AEs and any associated medical management
- Concomitant medications (including dietary supplements such as calcium, vitamin D, phosphorus)
- Assessment of medication adherence
- Tenofovir DF accountability
- Screening for pregnancy (urine screen)

Subjects who discontinue the study prior to the Week 96 Visit will complete all Week 96 assessments and procedures at an Early Drug Discontinuation Visit, to be completed within 72 hours of last dose of Tenofovir DF. Subsequent off-study therapy, if any, is at the discretion of the subject/physician and will not be provided by Gilead Sciences. Subjects who have received at least one dose of Tenofovir DF and permanently discontinue Tenofovir DF treatment will be followed for 24 weeks off treatment or up to initiation of standard of care treatment, whichever occurs first.

The study treatment will end after the each subject reaches Week 96.

6.5. Assessments for Premature Discontinuation from Study

If a subject discontinues Tenofovir DF (for example, as a result of an AE), every attempt should be made to keep the subject in the study and continue to perform the required study-related follow-up and procedures (see Section 6.6, Criteria for Discontinuation of Study Treatment). If this is not possible or acceptable to the subject or investigator, the subject may be withdrawn from the study.

6.6. Criteria for Discontinuation of Study Treatment

Study medication (Tenofovir DF) may be discontinued in the following instances:

- Intercurrent illness that would, in the judgment of the investigator, affect assessments of clinical status to a significant degree
- Unacceptable toxicity, as defined in the toxicity management section of this protocol, or toxicity that, in the judgment of the investigator, compromises the ability to continue study-specific procedures or is considered to not be in the subject's best interest
- Therapeutic failure
- Subject request to discontinue for any reason
- Subject non-compliance with taking Tenofovir DF or sustained inability to adhere to Tenofovir DF treatment plan
- Pregnancy during the study; refer to [Appendix 5](#)
- Discontinuation of the study at the request of Gilead, a regulatory agency or independent ethics committee (IEC)

6.7. End of Study

The end of study is defined as the completion of Tenofovir DF therapy and close-out monitoring by the last enrolled subject (e.g., last enrolled subject completes 96 Weeks of treatment and monitoring).

7. ADVERSE EVENTS AND TOXICITY MANAGEMENT

7.1. Definitions of Adverse Events, Adverse Reactions, and Serious Adverse Events

7.1.1. Adverse Events

An adverse event (AE) is any untoward medical occurrence in a clinical study subject administered a medicinal product, which does not necessarily have a causal relationship with the treatment. An AE can therefore be any unfavorable and/or unintended sign, symptom, or disease temporally associated with the use of a medicinal product, whether or not considered related to the medicinal product. AEs may also include pre- or post-treatment complications that occur as a result of protocol specified procedures, lack of efficacy, overdose, drug abuse/misuse reports, or occupational exposure. Preexisting events that increase in severity or change in nature during or as a consequence of participation in the clinical study will also be considered AEs.

An AE does not include the following:

- Medical or surgical procedures such as surgery, endoscopy, tooth extraction, and transfusion. The condition that led to the procedure may be an adverse event and must be reported.
- Pre-existing diseases, conditions, or laboratory abnormalities present or detected before the screening visit that do not worsen
- Situations where an untoward medical occurrence has not occurred (e.g., hospitalization for elective surgery, social and/or convenience admissions)
- Overdose without clinical sequelae, unless the subject is hospitalized (see Section 7.6.1)
- Any medical condition or clinically significant laboratory abnormality with an onset date before the consent form is signed and not related to a protocol-associated procedure is not an AE. It is considered to be pre-existing and should be documented on the medical history CRF.
- Uncomplicated pregnancy
- An induced elective abortion to terminate a pregnancy without medical reason

7.1.2. Serious Adverse Events

A **serious adverse event** (SAE) is defined as an event that, at any dose, results in the following:

- Death
- Life-threatening (Note: The term “life-threatening” in the definition of “serious” refers to an event in which the subject was at risk of death at the time of the event; it does not refer to an event that hypothetically might have caused death if it were more severe.)

- In-patient hospitalization or prolongation of existing hospitalization
- Persistent or significant disability/incapacity
- A congenital anomaly/birth defect
- A medically important event or reaction: such events may not be immediately life-threatening or result in death or hospitalization but may jeopardize the subject or may require intervention to prevent one of the other outcomes constituting SAEs. Medical and scientific judgment must be exercised to determine whether such an event is a reportable under expedited reporting rules.

Examples of medically important events include intensive treatment in an emergency room or at home for allergic bronchospasm; blood dyscrasias or convulsions that do not result in hospitalization; and development of drug dependency or drug abuse. For the avoidance of doubt, infections resulting from contaminated medicinal product will be considered a medically important event and subject to expedited reporting requirements.

The purposes of this study, in addition to the above criteria, the following must be reported as an SAE:

7.1.3. Clinical Laboratory Abnormalities and Other Abnormal Assessments as Adverse Events or Serious Adverse Events

Laboratory or imaging abnormalities without clinical significance are usually not recorded as AEs or SAEs. However, laboratory abnormalities (eg, renal or bone lab values, hematology, liver chemistry, urinalysis) or imaging abnormalities (eg, DEXA) that require medical or surgical intervention or lead to Tenofovir DF interruption, modification, or discontinuation must be recorded as an AE, as well as an SAE, if applicable. In addition, laboratory or other abnormal assessments (eg, electrocardiogram, x-rays, vital signs) that are associated with signs and/or symptoms must be recorded as an AE or SAE if they meet the definition of an AE or SAE as described in Sections 7.1.1 and 7.1.2. If the laboratory abnormality is part of a syndrome, record the syndrome or diagnosis (eg, anemia), not the laboratory result (ie, decreased hemoglobin).

For specific information on handling of clinical laboratory abnormalities in this study, please refer to [Appendix 4](#).

7.2. Assessment of Adverse Events and Serious Adverse Events

The investigator or qualified sub investigator is responsible for assessing AEs and SAEs for causality and severity, and for final review and confirmation of accuracy of event information and assessments.

7.2.1. Assessment of Causality for Tenofovir DF Treatment and Procedures

The investigator or qualified sub investigator is responsible for assessing the relationship to Tenofovir DF therapy using clinical judgment and the following considerations:

- **No:** Evidence exists that the adverse event has an etiology other than Tenofovir DF. For SAEs, an alternative causality must be provided (eg, pre-existing condition, underlying disease, intercurrent illness, or concomitant medication).
- **Yes:** There is reasonable possibility that the event may have been caused by the medicinal product (i.e., Tenofovir DF).

The site investigator or sub-investigator may further classify renal or bone AEs as an ADR or SADR, if an association of the clinical event to Tenofovir DF and the degree of AE seriousness can be ascertained. All SAEs (i.e., not limited to renal or bone events) will be reported.

It should be emphasized that ineffective treatment should not be considered as causally related in the context of adverse event reporting.

The relationship to study procedures (e.g., invasive procedures such as venipuncture or biopsy) should be assessed using the following considerations:

- **No:** Evidence exists that the adverse event has an etiology other than the study procedure.
- **Yes:** The adverse event occurred as a result of protocol procedures, (eg., venipuncture)

7.2.2. Assessment of Severity

Severity should be recorded and graded according to the GSI Grading Scale for Severity of Adverse Events and Laboratory Abnormalities ([Appendix 4](#)). For AEs associated with laboratory abnormalities, the event should be graded on the basis of the clinical severity in the context of the underlying conditions; this may or may not be in agreement with the grading of the laboratory abnormality.

7.3. Investigator Requirements and Instructions for Reporting Adverse Events and Serious Adverse Events to Gilead

Requirements for collection prior to Tenofovir DF initiation:

After informed consent, but prior to initiation of Tenofovir DF, the following types of events should be reported on the case report form (CRF/eCRF): all SAEs and AEs related to protocol-mandated procedures.

Adverse Events

Following initiation of Tenofovir DF, collect all bone and renal AEs, regardless of cause or relationship, until 30 days after last administration of Tenofovir DF must be reported to the CRF/eCRF database as instructed.

All bone and renal AEs should be followed up until resolution or until the adverse event is stable, if possible. Gilead Sciences may request that certain AEs be followed beyond the protocol defined follow up period.

Serious Adverse Events

All bone and renal SAEs, regardless of cause or relationship, that occurs after the subject first consents to participate in the study (i.e., signing the informed consent) and throughout the duration of the study, including the protocol-required post treatment follow-up period, must be reported to the CRF/eCRF database and Gilead Drug Safety and Public Health (DSPH) as instructed. This also includes any bone and renal SAEs resulting from protocol-associated procedures performed after informed consent is signed.

Any SAEs and deaths that occur after the post treatment follow-up visit but within 30-days of the last dose of Tenofovir DF, regardless of causality, should also be reported.

Investigators are not obligated to actively seek bone and renal SAEs after the protocol defined follow up period, however, if the investigator learns of any SAEs that occur after study participation has concluded and the event is deemed relevant to the use of Tenofovir DF, he/she should promptly document and report the event to Gilead DSPH.

- All bone and renal AEs and (S)ADRs and all SAEs (not limited to bone and renal events) will be recorded in the CRF/eCRF database within the timelines outlined in the CRF/eCRF completion guideline.
- At the time of study start, SAEs will be reported using a paper serious adverse event reporting form. During the study conduct, sites may transition to an electronic SAE (eSAE) system. Gilead will notify sites in writing and provide training and account information prior to implementing an eSAE system.

Serious Adverse Event Paper Reporting Process

- All pre-specified SAEs will be recorded on the serious adverse event report form and submitted by faxing or emailing the report form within 24 hours of the investigator's knowledge of the event to the attention of Gilead DSPH or to the designated CRO.

CRO (TBD)

Contacts (TBD)

Gilead Sciences DSPH
Representative:

[contact]
E-mail: [contact]

Electronic Serious Adverse Event (eSAE) Reporting Process

- Site personnel record all SAE data in the eCRF database and from there transmit the SAE information to Gilead DSPH within 24 hours of the investigator's knowledge of the event. Detailed instructions can be found in the eCRF completion guidelines.

- If for any reason it is not possible to record the SAE information electronically, i.e, the eCRF database is not functioning, record the SAE on the paper serious adverse event reporting form and submit within 24 hours as described above.
- As soon as it is possible to do so, any SAE reported via paper must be transcribed into the eCRF Database according to instructions in the eCRF completion guidelines.
- If an SAE has been reported via a paper form because the eCRF database has been locked, no further action is necessary.
- For fatal or life-threatening events, copies of hospital case reports, autopsy reports, and other documents are also to be submitted by e-mail or fax when requested and applicable. Transmission of such documents should occur without personal subject identification, maintaining the traceability of a document to the subject identifiers.
- Additional information may be requested to ensure the timely completion of accurate safety reports.
- Any medications necessary for treatment of the SAE must be recorded onto the concomitant medication section of the subject's CRF/eCRF and the event description section of the SAE form.

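### Protocol 7.3 gives conflicting SAE scopes: its main SAE paragraph covers only bone and renal SAEs, while the neighbouring text and four other provisions cover all SAEs

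*Protocol*

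**What the plan says.** The SAE paragraph of Protocol 7.3 requires reporting of "All bone and renal SAEs, regardless of cause or relationship, that occurs after the subject first consents to participate in the study". It carries that duty through the whole study, "including the protocol-required post treatment follow-up period, must be reported to the CRF/eCRF database and Gilead Drug Safety and Public Health (DSPH) as instructed". Two further sentences in the paragraph, on procedure-related events and on the end of active surveillance, repeat the bone and renal limit.

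Two sentences in the same paragraph have no organ limit. One covers "Any SAEs and deaths that occur after the post treatment follow-up visit but within 30-days of the last dose of Tenofovir DF". The other is passive and applies "if the investigator learns of any SAEs that occur after study participation has concluded and the event is deemed relevant" to the drug.

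Other text is broad. Protocol 7.2.1 states: "All SAEs (i.e., not limited to renal or bone events) will be reported". The first bullet after the SAE paragraph in 7.3 says that "all SAEs (not limited to bone and renal events) will be recorded in the CRF/eCRF database". The electronic route in 7.3 covers all SAE data and sends it to drug safety within 24 hours. The paper route, in use at study start, reads: "All pre-specified SAEs will be recorded on the serious adverse event report form". Protocol 6.2.1 asks for any SAE during screening, and Protocol 8.6.2 plans a summary of serious events across all system organ classes.

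**The concern.** A site needs to know which SAEs to send, to whom and for how long. The sentence that answers all three is the narrow one. A coordinator who follows it alone could reasonably conclude that a serious infection or a serious hepatic event is outside the duty to notify drug safety.

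This matters because a foreseeable serious event after stopping this drug is hepatic. Protocol 7.5.7 acknowledges severe and fatal exacerbations of hepatitis after HBV therapy is discontinued and calls for at least six months of monitoring. Under Protocol 7.4 the sponsor judges expectedness and makes expedited reports, and it can do so only for events it receives. The SAP's summaries and listing of SAEs likewise assume that SAEs of every kind were collected.

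**Working it through.** No plan figure needs reproducing. The check sets the SAE statements side by side and then measures the period over which they diverge.

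| Place in Protocol | SAEs covered | Collection window stated | Recipient stated |
|---|---|---|---|
| 7.3, SAE paragraph, main sentence | bone and renal | consent through post-treatment follow-up | CRF/eCRF and drug safety |
| 7.3, pre-treatment rule | all | consent to first dose | CRF/eCRF |
| 7.3, 30-day sentence | any, and deaths | after the follow-up visit, within 30 days of last dose | none |
| 7.3, post-study sentence | any the investigator learns of and deems relevant | after participation ends | drug safety |
| 7.3, first bullet | all | none | CRF/eCRF |
| 7.3, paper route | pre-specified | none (24 hours from knowledge) | drug safety or CRO |
| 7.3, electronic route | all | none (24 hours from knowledge) | eCRF, then drug safety |
| 7.2.1 | all | none | none |
| 6.2.1 | any | consent to first dose | AE CRF |
| 8.6.2 | all organ classes | planned summary | not applicable |

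Only the main sentence of the SAE paragraph gives both a window through post-treatment follow-up and drug safety as recipient, and it is limited to bone and renal events. The broad statements omit the window, the recipient or both.

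**Length of the divergence off treatment.**
- Follow-up after permanent discontinuation is 24 weeks, or until other treatment starts if sooner (Protocol 3.2; SAP 1.2): 24 × 7 = 168 days.
- The 30-day sentence is credited here with the whole first 30 days off drug.
- Remainder: 168 − 30 = 138 days (days 31 to 168), and 138/168 = 82%.
- Under 7.2.1 or the first bullet of 7.3, which set no time limit, the remainder is 0 days.

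The period without an explicit active duty is therefore 0 to 138 days per subject, depending on which text the site follows and when other therapy starts.

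**On treatment.** The SAE paragraph read alone gives no duty to notify drug safety of a non-bone, non-renal SAE. The 30-day sentence does not help, because it begins after the post-treatment follow-up visit. Pregnancy losses are an exception, since Protocol 7.6.2.1 requires them within 24 hours.

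**Effect on the SAP outputs.** SAP 7.1.5.1 ends the treatment-emergent period at last dose plus 30 days. The SAE summaries in SAP 7.1.6 (Tables 19.9 and 19.10) are treatment-emergent. An on-treatment SAE that is not collected would be missing from them. An SAE from day 31 onward would not enter them under any reporting rule; among the SAE displays it could be missing only from Listing 15.2. The counts and listing of deaths are separate outputs.

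**The case against.** The strongest reply is that the explicit clarifications all point one way. The bullets belong to the same Section 7.3 and follow the narrow paragraph directly. They say SAEs are not limited to bone and renal events, and the electronic route sends all of them to drug safety within 24 hours. Protocol 6.2.1, 7.2.1 and 8.6.2 agree. This stands: the intended design is all SAEs, and the defect is wording that contradicts it. It does not remove the conflict. The first bullet concerns entry in the database on timelines held in a separate guideline, and the paper route used at study start carries a qualifier that the electronic route lacks.

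Four stronger readings are tempting and should not be drawn.

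- **That 82% of follow-up is unmonitored for SAEs.** It is an upper bound on one literal reading. Protocol 7.5.7 also says patients should be placed on commercially available HBV therapy after stopping, which ends follow-up. The 30-day sentence adds events ("within 30-days of the last dose of Tenofovir DF, regardless of causality, should also be reported") and is not stated as a cap.
- **That 28 subjects were exposed.** SAP 1.4 and 2.1 give 30 enrolled and two completing 96 weeks, so 30 − 2 = 28 did not complete. The SAP attributes this to early study termination and does not say how many entered untreated follow-up.
- **That off-treatment hepatitis goes unobserved.** Protocol 7.5.7.2 sets return visits, confirmatory tests and follow-up for up to six months. SAP 7.2.2.3 defines post-treatment exacerbation, and Table 25 reports it. That is not SAE reporting, but the events are looked for.
- **That the pre-specified SAEs were never defined.** Protocol 7.1.2 introduces a study-specific list whose entries are not visible and may have been lost from the public text. No weight is placed on their absence.

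**Conclusion.** Protocol 7.3 contains two incompatible SAE scopes, and the narrower one sits in the sentence that sets window and recipient. On that sentence alone, non-bone, non-renal SAEs carry no explicit duty to notify drug safety while on treatment, nor from day 31 to week 24 off treatment. The off-treatment part is at most 138 of 168 days if the 30-day sentence is read as covering the first 30 days, and it shortens if other HBV therapy begins.

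The result rests on a site following the paragraph literally. A site following 7.2.1 or the first bullet of 7.3 would leave no SAE out. The documents do not show that any SAE was missed. The risk to the treatment-emergent SAE tables comes from on-treatment losses only; the risk from later losses is to the SAE listing and expedited safety reporting. The correction is worth making because the exposed events include the serious hepatic ones that the protocol itself anticipates.

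**What to change.** In Protocol 7.3:

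1. Remove the bone and renal limit from the three SAE sentences that carry it, so that one scope (all SAEs) and one window (consent through the protocol-required post-treatment follow-up) apply. The 30-day sentence can remain for events after the last visit.
2. Make the paper route cover the same SAEs as the electronic route, by deleting the pre-specified qualifier or pointing it to a definition with that scope.

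Because the SAP gives the last visit as April 2018, the practical steps now are:

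3. Use the reconciliation of the clinical and drug safety databases in SAP 7.1.4 to look for non-bone, non-renal SAEs held in one and not the other. Reconciliation cannot show an event absent from both, so ask sites to confirm that none is outstanding.
4. Disclose the inconsistency in the study report, with the number of subjects who entered untreated follow-up and its length.

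The cost is wording, one site query and a short paragraph in the report. No new data collection is implied, since Protocol 6.2.1, 7.2.1, 8.6.2 and the bullet in 7.3 already call for all SAEs.
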